23.4. Exclusion of Particular Information

All SADEs that occurred later than the 3M-FU, or more than 121 days after implantation, if 3M-FU was outside the required visit window, are not considered.

23.5. Descriptive Analyses

Absolute and relative frequencies and additionally the two-sided 97.5% CI are presented.

23.6. Hypotheses & Statistical Tests

CIP chapter 8.3.1.1 Group A: Ilvia family related SADE-free rate through 3 months

Null hypothesis: $H_{0_plexa} : Plexa_{SADE_free} \leq 90\%$

Alternative hypothesis: $H_{A_plexa} : Plexa_{SADE_free} > 90\%$

CIP chapter 11.1. Statistical design, methods and analytical procedures

For both primary hypotheses exact binomial tests are carried out.

CIP chapter 11.2. Sample size

A correction for multiple testing is considered by adjusting the significance level.

CIP chapter 11.3. Level of significance and the power of the study

The 2-sided level of significance is $\alpha = 2.5\%$ for each alternative hypothesis (1-sided 1.25% significance level)

A one-sided exact binomial test is carried out for the significance level 1.25%. Additionally, a two-sided 97.5% confidence interval for an exact binomial test is calculated.

23.7. Alternative analysis (as suggested by the study objective)

In the definition of the hypothesis, it is stated that endpoints are analyzed if they occur before the 3-months FU (see above, 23.2). However, in section 7 the CIP states that safety through 3 months is the primary study objective.

7.1.1 Primary Objectives

...

7.1.1.2 Group B: Plexa related safety through 3 months

This objective of the clinical investigation is to confirm the clinical safety of the Plexa ICD lead by the analysis of the Plexa related SADEs **within 3 months after implantation.**

A way to analyse the data that is more closely oriented at the study objective than the method described above is a Kaplan-Meier analysis. The Kaplan-Meier estimated rate at 91 days represents the best estimate of the target variable.

All patients of the Plexa analysis set will be included until the time of a first event or censoring due to study discontinuation.

24. Secondary EP: Rate appropriate RV sensing Plexa

24.1. Analysis set

All analyses are performed for the Plexa analysis set¹⁰¹.

CIP chapter 11.1 Statistical design, methods and analytical procedures

All endpoints are analysed per-protocol (PP), whereby the analysis sets are defined for each hypothesis separately.

CIP chapter 8.3.2.2.1 Rate of appropriate right ventricular sensing at 3-month follow-up

Only the evaluation of the 3-month follow-up is taken into account towards data analysis of this endpoint. Only patients with measurements performed at the 3-month follow-up will be included in this analysis set. Specifically, the percentage of patients with an appropriate RV sensing at the 3-month follow-up will be determined.

All analyses are performed for patients with non-missing RV sensing data at the 3-month follow-up.

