Patients in both groups A and B: It is recommended that patients are implanted with both investigational devices, the Ilivia ICD family **and** Plexa ICD lead, Figure 5. Such patients can belong to both study groups and should then complete all follow-ups as required by both groups. The participation in both groups instead of only in group A or in group B can be freely chosen by the investigator based on his/her medical opinion. However, the investigation should be compliant with the study protocol for group A, group B or both, respectively.

The enrollment of patients in both study groups will be stopped independently. The project management of the BIO|MASTER.Ilivia Family / Plexa study will inform all investigators in advance in written form about the stop of enrollment of patients to both groups A and B.

After 105 patients have been enrolled into group A, or 185 into group B, further patients can receive both Ilivia and Plexa implants, but can only be enrolled into the group which is still open for enrollment. These patients are not subject to CIP required procedures related to endpoints of the group into which they have not been enrolled, and if endpoints are recorded by oversight of the investigator, they will be excluded from the analysis.

Furthermore, in case a patient enrolled in both groups, is exited from one of the groups, only data for the still active group will be provided and used for analysis from that point in time on.

[figure not shown]

Fig. 5: Overlap of both study groups. Patients implanted with an ICD device of the Ilivia family and a Plexa ICD lead can belong to both groups A and B

A study duration of about 14 months enrollment plus 6 months FU = 20 months is expected in total. First Patient In (FPI) is expected for beginning of June 2016. Last Patient In can be expected for end of July 2017 (LPI), which means that the last patient will leave the study end of January 2018 (LPO, Last Patient Out).

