8.5.11 Lead measurements at each follow-up

The system performance and right ventricular lead performance is evaluated at the end of the implantation procedure and **at the end** of each follow-up for both groups **A** and **B** by either manually or automatically triggered lead measurements. For this purpose the investigator performs the threshold tests, determines pacing impedance and painless shock impedance and performs P/R-wave amplitude measurements in all available channels. In the RA and RV the pulse width must be 0.4 ms, in the LV any pulse width can be chosen. For patients in **group A** measurement of all LV pacing vectors is **mandatory** prior to programming of the MPP feature, either after implantation or at time of Pre-hospital discharge. Pacing polarities of the LV

channel must be documented. For patients of **group B**, only measurement of the right channel is required (in DX leads also sensing measurements in the atrial channel).

In group A and B the appropriate sensing and pacing should be evaluated at the 3-month follow-up. In **group A** evaluation should be done in all available channel. In **group B** only the RV channel has to be assessed, for DX leads additionally also the atrial sensing. For the evaluation it is necessary to record 10 consecutive intrinsic beats and 10 consecutive pulses with markers on the IEGM, respectively. The "freeze" button needs to be pressed to store the IEGM electronically. The sensing of the lead will be assessed as "adequate" (= the device sensed the current rhythm correctly) or inadequate. In the ventricles the additional option "no intrinsic rhythm" (= patient is fully paced) is available to describe if an evaluation of sensing is not possible. In case the sensing is considered inadequate, the reason "oversensing", "undersensing", "not measurable" (= quality/content of IEGM does not allow any discrimination if senses are correct (e.g. lead dislodgement)) or "other" will be determined. The pacing of the lead will be assessed as adequate (=successful stimulation) or inadequate. In case the pacing is considered inadequate, the reason for the evaluation is required. Possible options are "non-capture" (= no evidence of depolarization after pacing), "no output" (= failure to pace: impulses are generated by the device but is not transferred to the myocardium), "not measurable" (= quality/content of IEGM does not allow any discrimination if stimulation is successful) or "other".

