8.8.4 Drop-out criteria

8.8.4.1 Mandatory drop-out according to protocol

The investigator shall exclude a patient due to the following reasons (defined as drop-out according to protocol):

- **Group A:** Patient is not implanted with a member of the Ilivia ICD family for any reason
- **Group A:** Patient in whom explantation or replacement of the Ilivia ICD is performed
- **Group B:** Patient in whom implantation of Plexa ICD lead was planned but not performed
- **Group B:** Patient in whom explantation, replacement or repositioning of the Plexa ICD lead is performed
- Patient undergoes heart transplantation or receives ventricular assist device during the course of the study.

If a patient participates in both groups, drop-out in one group does not result in drop-out of the other group, thus the patient can continue participation in the other study group.

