6. Report all adverse events. In case of a serious adverse event, or adverse device effect (ADE), please provide the information immediately to BIOTRONIK, and inform the ethical committee, if required. Report adverse events within the indicated timelines (see section 18.9). If the Ilivia ICD or Plexa ICD lead is exchanged or repositioned the follow-up schedule is adapted as described in section 9.8 "Interim Intervention". Report adverse events within the indicated timelines (see section 18.9).

9.5 3-month follow-up

Three months (\pm 30 days) after the implant procedure, the patient has to return to the hospital for assessment of the implanted system. The investigator reviews the system performance and adjusts the programmed parameters as necessary to optimize the ICD functions. The requirements of this procedure are listed below:

1. Reprogramm ICD settings as applicable to optimize ICD/CRT-D functions
2. The following data have to be measured at the end of the follow-up (same as during implantation) with the final programmed ICD settings:
 - Pacing thresholds measured manually or triggered automatically in all channels (**group A**) or RV only (**group B**). For patients in **group A** with MPP activated, both LV vectors have to be measured accordingly. In all channels the pulse width must be 0.4 ms.
 - P/R-wave sensing amplitude (mean value) of all channels (or RV lead only (**group B**)), including also atrial sensing amplitude in DX leads.

- Pacing impedance of all channels (or RV lead only (**group B**)). For the LV channel, measurement of the pacing threshold automatically also provides impedance measurement values.
 - Painless shock impedance
 - Pacing polarities of the LV channel (CRT-D devices only (**group A**))
 - Evaluate the system performance at end of follow-up for all channels (**group A**) or the RV channel and for DX lead also atrial sensing channel (**group B**). It is recommended to record 10 consecutive intrinsic beats (sensing test) and 10 consecutive pulses (threshold test) with markers on the IEGM. Press the "freeze" button to store the IEGM electronically.
3. Document device statistics for CRT-D patients (CRT-D patients only).
 4. Document changes in programming of MPP settings, if applicable (**group A**, CRT-D patients only).

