9.8 Interim Intervention: Lead / Device Revision

For all revisions, an interim intervention eCRF has to be completed. Information has to be provided on the nature of the event, the affected device and any newly implanted devices. If the ICD is repositioned or the LV lead is revised and a Sentus QP lead remains active after the revision (**group A**), lead measurements have to be performed at the end of the revision as defined in the 3-month follow-up. Furthermore in case of CRT-D, changes on MPP programming have to be documented (**group A**), if applicable.

An Adverse Event Report has to be completed for every interim intervention.

In case of any revision with invasive corrective action, the following follow-up schedule applies:

- Patients are drop-outs in case of Ilivia and/or Plexa explantation or exchange and/or Plexa repositioning after initial implantation. In case patients participate in both groups A and B, drop-out is only applicable for the respective group.
- In case of Ilivia repositioning at any time after implantation, the initial follow-up schedule remains unchanged. The data will be used for further analysis.
- In case of unsuccessful implantation of Ilivia and/or Plexa, the patient is a drop-out patient. No further follow-ups are performed. Patients participating in both groups A and B are only considered drop-out patients in the respective group.
- In case of revision of a non-investigational device at any time after implantation, the initial follow-up schedule remains unchanged. The data will be used for further analysis.

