25.1. Analysis set

All analyses are performed for the Plexa analysis set¹⁰².

CIP chapter 11.1 Statistical design, methods and analytical procedures

All endpoints are analysed per-protocol (PP), whereby the analysis sets are defined for each hypothesis separately.

CIP chapter 8.3.2.2.2 Rate of appropriate right ventricular pacing at 3-month follow-up

Only the evaluation of the 3-month follow-up is taken into account towards data analysis of this endpoint. Only patients with measurements performed at the 3-month follow-up will be included in the endpoint.

All analyses are performed for patients with non-missing RV pacing data at the 3-month follow-up.

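### The Plexa sensing and pacing analysis sets in SAP 24.1 and 25.1 do not apply the CIP rule on exit from group B, so 3-month readings taken after a lead revision can be counted (minor)

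*SAP*

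**What the plan says.** **Filters.** SAP 24.1 starts from the Plexa analysis set and adds: "All analyses are performed for patients with non-missing RV sensing data at the 3-month follow-up". SAP 25.1 does the same for pacing: "All analyses are performed for patients with non-missing RV pacing data at the 3-month follow-up". SAP 7.3 (footnote 6) builds the Plexa set from consent, eligibility, group B or AB at implantation, and contact with a Plexa lead. It contains no condition on group B termination.

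**Exit from group B.** CIP 8.8.4.1 lists as a mandatory group B drop-out: "Patient in whom explantation, replacement or repositioning of the Plexa ICD lead is performed". CIP 9.8 agrees: "Patients are drop-outs in case of Ilivia and/or Plexa explantation or exchange and/or Plexa repositioning after initial implantation". For a patient in both groups, CIP 8.8.4.1 adds that "drop-out in one group does not result in drop-out of the other group".

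**Data after exit.** CIP 8.1 says that for a patient who has left one of the two groups, "only data for the still active group will be provided and used for analysis from that point in time on". CIP 11.12 points to section 8.1 for further exclusions. The excerpt of 11.12 in SAP 5.5 omits that pointer. CIP 11.10, item 1, says that data after a lead explant, repositioning or exchange are used for further analysis, and refers to 9.8 for the schedule.

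**Assessment in group A.** CIP 8.5.11: "In group A and B the appropriate sensing and pacing should be evaluated at the 3-month follow-up". CIP 9.5 sets the scope for group A: "Evaluate the system performance at end of follow-up for all channels". The SAP reads `fu3_perf_rv_sens` and `fu3_perf_rv_pac` for the Ilivia set (13.2) and for the Plexa endpoints (24.2, 25.2).

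**The concern.** Two gaps follow.

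1. A patient in both groups with an early Plexa revision satisfies the SAP 24.1 and 25.1 filters if a 3-month RV reading exists. That reading may come from a repositioned Plexa lead or from a different RV lead. It may count as a success for the lead position that was given up. A programmer following CIP 8.1 would exclude the patient, while one following the SAP text or CIP 11.10 would not. The plan therefore allows two denominators for both tested secondary endpoints of group B.

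2. If the exit is applied, the rates describe only leads still in place and assessed. CIP 8.3.2.2 defines them that way openly. However, a lead revised early for lost sensing or capture then leaves both numerator and denominator, and nothing beside the rate shows this. Early terminations are listed and counted by reason and group (SAP 7.2, 8.2), but not by lead function and not next to these rates. What is at stake is how the rates are read, not whether the study passes.

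**Working it through.** **The plan's own figure.** With a null rate of 90%, an assumed rate of 97% and one-sided alpha 1.25%, n = 166 allows at most 8 events. The exact level is 1.215% and the power 93.6%. 166/0.9 = 184.4, so 185 are enrolled. The stated group B size is reproduced. The documents give no sample size for the secondary tests, so 166 is used below as a working denominator.

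**Secondary test (SAP 24.6, 25.6).** The null rate is 93%, one-sided level 2.5%, exact binomial. The largest allowed number of failures c satisfies P(X ≤ c | n, 0.07) ≤ 0.025:

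| n | allowed failures |
|---|---|
| 144–163 | 4 |
| 164–182 | 5 |
| from 183 | 6 |

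Exact levels are 1.00% at n = 162, 2.42% at n = 164 and 2.22% at n = 166.

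**Assumed counts.** The documents give neither an early Plexa revision rate nor the size of the A/B overlap. One anchor is the predecessor lead study in CIP 5.2.5: (3+1)/(75+84) = 4/159 = 2.5%, about 4 of 166. These were dislodgement complications and are not stated to be revisions. An upper scenario is 8 of 167 (4.8%) from CIP 5.2.2, about 8 of 166; the timing and management of those events are not given. The overlap is at most 105/185 = 57%.

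**Effect of gap 1 on the rate.** Keeping m post-revision patients, all rated adequate, beside n measured patients raises the rate by m/(n+m) × (1 − rate). Take 2 inadequate leads among those never revised:
- 4 revised, none kept: 160/162 = 98.8% (exact 95% lower limit 95.6%, 4 failures allowed).
- 4 revised, 2 kept: 162/164 = 98.8% (lower limit 95.7%, 5 failures allowed).
- 8 revised, none kept: 156/158 = 98.7%; all 8 kept: 164/166 = 98.8%.
- With a rate of only 93% and 2 kept: 2/164 × 0.07 = 0.09 point.

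**Effect of gap 1 on the test.** Let the true rate over all implanted leads be 93%, with 2.5% of leads revised, every revision a failure of the tested function, and 57% of revised patients kept as adequate. The failure probability among leads in place is (0.07 − 0.025)/0.975 = 4.6%. The number revised varies at random (simulation). Pass probability without and with the kept patients:

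| N | not kept | kept |
|---|---|---|
| 160 | 14.9% | 14.9% |
| 166 | 15% | 21% |
| 175 | 19.6% | 19.7% |

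At N = 180 there is no change beyond simulation noise. A jump like that at 166 recurs near N = 185. At N = 166 the change is 4.4% to 6.7% if half the revisions are failures of the tested function, and 2.2% to 3.6% if a quarter are. The jump arises because removing about 4 patients from 166 crosses the step from 5 to 4 allowed failures, and keeping 2 of them crosses back.

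**Gap 2.** Same counts, with revised leads counted as not appropriate:
- 4 revised: 160/166 = 96.4% (exact 95% CI 92.3–98.7%), against 98.8% measured-only.
- 8 revised: 156/166 = 94.0%, against 98.7%.

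Each such lead costs 1/166 = 0.6 point.

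**The case against.** **The rule is already in the CIP.** CIP 8.1 states it, CIP 11.12 points to it, and SAP 24.1 cites per-protocol analysis. This stands in part, because the intention is recoverable. It does not close the gap. CIP 11.1 says the sets are defined separately for each hypothesis, the definition given omits the exit, SAP 5.5 drops the pointer, and CIP 11.10 supports the opposite reading.

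**The SAP did not forget a filter that it uses elsewhere.** This stands. `enddate_Plexa_SAR` enters primary endpoint 2 only in footnote 99, as a minimum follow-up of 61 days. It is not used there to drop post-exit data.

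**The measured-only rate is prespecified.** This stands. The tests hold their level for that parameter. A reader might infer from the 15–21% pass probabilities that the type I error is inflated. The documents do not support that, since those figures refer to a rate over all implanted leads that the trial does not test. They also assume a true rate of exactly 93% and that every revision is a failure of the tested function.

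**Failed leads are counted elsewhere.** This largely stands. Device-related revisions meeting CIP 18.11 count in primary endpoint 2 and in the Kaplan-Meier analysis of SAP 23.7. Securely procedure-related ones count in none of the three group B endpoints, by the CIP's own choice.

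**57% overlap is extreme.** This stands. It needs every group A patient to be in group B, yet group A admits upgrades and exchanges, which group B excludes.

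**Conclusion.** The gap in SAP 24.1 and 25.1 is real: as written, the filters admit readings that CIP 8.1 excludes, and CIP 11.10 leaves room to defend that. It concerns only patients in both groups, because participation of a group B-only patient ends at the revision.

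The consequence is minor. In the scenarios worked, the rate moves by about 0.1 point or less. The test can gain one allowed failure only when the denominator lies near a step, such as 166 or 185; at 160, 175 or 180 the pass probability is essentially unchanged. The sensing denominator will not be known in advance, since patients without intrinsic rhythm or without an assessment are left out.

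The missing companion figure matters more for interpretation (96.4% against 98.8% with 4 assumed revisions, all bearing on the tested function). It is a supportive addition and not a departure from the CIP. A reader might also infer that the study's conclusion is at risk. It is not, because CIP 11.5 rests pass/fail on the two primary hypotheses alone. All sizes depend on assumed revision counts and overlap.

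**What to change.** 1. In SAP 24 and 25, require `fu3_visdate` ≤ `enddate_Plexa_SAR`. If the dates are equal, count the assessment only if it preceded the revision. CIP 8.8.5 ties the end date to the revision date for replacement and repositioning but does not name explantation, so confirm that the variable carries the explant date in that case too.
2. Reconcile CIP 11.10 with 8.1, 8.8.4.1 and 9.8 on whether data after a Plexa revision are used, and for which group.
3. Keep the measured-only tests as the confirmatory analyses. Beside each rate, show the number and reasons of Plexa revisions before the 3-month visit. Add a rate with exact 95% CI that counts as not appropriate the leads revised for a reason bearing on that function. Document the assignment of each revision to sensing, pacing, both or neither before database closure.
4. Do not test the supportive rate against 93%. The CIP does not derive that figure, and the predecessor's 98.4% appears to be measured-only: it cannot arise from all 75 enrolled (73/75 = 97.3%, 74/75 = 98.7%).

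Cost: SAP text, one condition on an existing variable, two descriptive variables from the interim intervention and adverse event forms, and a CIP clarification. CIP 13 classes changes affecting data analysis as substantial. The downside is a less favourable supportive figure and some judgement in assigning revisions to a function.

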24.2. Variables

CIP chapter 8.3.2.2.1 Rate of appropriate right ventricular sensing at 3-month follow-up

*The parameter of interest $Plexa_{Sensing}$ is the rate of patients with appropriate sensing which will be calculated by $Plexa_{Sensing} = (\text{Number of patients with appropriate sensing (Sensing}_{app}) / \text{divided by number of patients with sensing measurements performed}) * 100\%$.*

Data file, identifier patient_display_id_full	Descriptive	Variable name	Variable label, NEW prefix added to all labels "3mFU data: "	Variable level	Nominal values
fu_3_month_device_data	No	fu3_perf_rv_sens	Adequate RV sensing	nominal	Yes / No

24.3. Treatment of Missing and Spurious Data

See general definitions in chapter 5.4.

24.4. Exclusion of Particular Information

See general definitions in chapter 5.5.

24.5. Descriptive Analyses

See general definitions in chapter 5.1.

24.6. Hypotheses & Statistical Tests

Null hypothesis: $H_{0_Sensing} : Plexa_{Sensing} \leq 93\%$

Alternative hypothesis: $H_{A_Sensing} : Plexa_{Sensing} > 93\%$

No multiplicity adjustment is performed for the secondary hypotheses. Thus a one-sided exact binomial test is carried out for the significance level 2.5%. Additionally, a two-sided 95% confidence interval for an exact binomial test is calculated.

¹⁰¹ analysis_set_Plexa_SAR = Yes

25. Secondary EP: Rate appropriate RV pacing Plexa

